1.1 Synopsis

Protocol Title: A Phase 3, Multicenter, Randomized, Double-blind, Placebo-controlled Study to Evaluate the Efficacy and Safety of Apremilast (AMG 407) in Japanese Subjects with Palmoplantar Pustulosis (PPP)

Short Protocol Title: Phase 3, Randomized Study of Apremilast in Japanese Subjects with Palmoplantar Pustulosis

Study Phase: 3

Indication: Treatment of palmoplantar pustulosis

Study Rationale

The characteristic histopathological features of palmoplantar pustulosis (PPP) exhibit intraepidermal infiltration of polymorphonuclear neutrophils forming pustules. Although the mechanisms of neutrophil chemotaxis towards the epidermis are unknown, there are several publications that support a role for interleukin (IL)-17 as a promoter of neutrophil accumulation and activation (Yamamoto, 2009; Hagforsen et al, 2010). Patients with PPP have both elevated serum tumor necrosis factor (TNF)-α, IL-17, IL-22, and IL8 levels and elevated neutrophil and Th17 gene expression in the pustular skin (IL-8, IL-17A, IL-36G, IL-12A [p40], IL-17F, IL-22, IL-23B [p19], DEFB4A, and TNF-α) (Murakami, 2011). Eccrine ducts, keratinocyte, and more inflammatory cell involvement is also suggested in PPP pathogenesis (Hagforsen et al, 2010; Murakami et al, 2014; Murakami et al, 2017).

Although corticosteroids, active vitamin D3 ointments, and phototherapy (ultraviolet [UV] radiation therapy) are common PPP treatments, evidence showing their efficacy in moderate to severe PPP cases is quite limited, highlighting the need for optimal, convenient, and targeted therapeutic options for the disease (Kobayashi et al 2010). By inhibiting phosphodiesterase-4 (PDE4), an enzyme prevalent in immune cells, apremilast is expected to inhibit the production of IL-17, IL-8, and several other inflammatory cytokines related to PPP pathogenesis.

The efficacy of apremilast has also been reported in patients with synovitis, acne, pustulosis, hyperostosis osteitis (SAPHO) syndrome (Adamo, 2018). One form of SAPHO syndrome, pustulotic arthro-osteitis (PAO), is a known complication of PPP, suggesting that apremilast may be an effective treatment in PPP patients with or without PAO (Sonozaki et al, 1981; Okubo, 2012; Okuno et al, 2018).

Protocol Number: 20200195

Date: 15 April 2022 Page 10 of 99

Apremilast studies, CC-10004-PSOR-005, CC-10004-PSOR-008 (hereafter referred to as ESTEEM-1), and CC-10004-PSOR-009 (hereafter referred to as ESTEEM-2), showed improvement of palmoplantar disease status in subjects with palmoplantar psoriasis, a closely related dermatological condition (Bissonnette et al, 2016). Efficacy was also demonstrated in Study CC-10004-BCT-002 for oral ulcers in subjects with Bechet's Disease (BD) in which IL-17 and neutrophils play important roles (Hatemi et al, 2019).

In a randomized, double-blind, placebo-controlled phase 2 study in Japan (Study CC-10004-PPP-001 [20200055]), apremilast showed efficacy in PPP treatment and safety and tolerability data was consistent with the known safety profile of apremilast. The phase 3 study is intended to confirm the risk-benefit balance of apremilast in the treatment of PPP in Japanese patients.

Objectives and Endpoints/Estimands

Objectives	Endpoints						
Primary							
To evaluate the efficacy of apremilast 30 mg twice daily (BID) compared with placebo in subjects with PPP	 Achieving at least 50% reduction from baseline in Palmoplantar Pustulosis Area and Severity Index (PPPASI) total score (PPPASI-50) at week 16 						
Secondary							
To evaluate the efficacy of apremilast 30 mg BID compared with placebo in subjects with PPP	 Change from baseline in PPPASI total score at week 16 Change from baseline in Palmoplantar Pustulosis Severity Index (PPSI) total score at week 16 Change from baseline in subject's Visual Analogue Scale (VAS) assessment for PPP symptoms (pruritis and pain/discomfort) at week 16 Change from Baseline in Dermatology Life Quality Index (DLQI) total score at week 16 						
To evaluate the safety and tolerability of apremilast 30 mg BID compared with placebo in subjects with PPP	Treatment-emergent adverse events, serious treatment-emergent adverse						

Protocol Number: 20200195

Date: 15 April 2022 Page 11 of 99

events, and adverse events of interest • Clinically significant changes in body weight, vital signs, and laboratory abnormalities
--

Primary Estimand

The primary efficacy endpoint is the achievement of PPPASI-50 at week 16 and the main estimand is the difference between apremilast 30 mg BID and placebo in the proportion of PPPASI-50 responders at week 16 based on the intent-to-treat (ITT) population including all randomized subjects, where subjects who discontinue investigational product (IP) due to lack of efficacy, adverse event, or use of protocol-prohibited medication are considered treatment failures.

- The target population of interest is Japanese subjects with PPP defined through the inclusion/exclusion criteria.
- The primary endpoint is the achievement of PPPASI-50 at week 16.
- Intercurrent events (IEs) are IP discontinuation due to lack of efficacy, adverse event, or protocol-prohibited medication use. A subject will be considered a non-responder after any of the IEs.
- The summary measure is the difference in proportion of responders.

Missing values of the data in which the treatment failures are considered as non-responders will be imputed using multiple imputation (MI) method.

Secondary Estimand(s)

The main estimand for the secondary efficacy endpoints is the difference in change from baseline at week 16 in PPPASI total score, PPSI total score, subject's VAS assessment for PPP symptoms (pruritus and pain/discomfort), and DLQI total score based on the ITT population in which subjects who discontinue the IP due to lack of efficacy, adverse event, or use of protocol prohibited medication are considered as treatment failures.

- The target population of interest is Japanese subjects with PPP defined through the inclusion/exclusion criteria.
- The secondary endpoints are the change from baseline at week 16 in PPPASI total score, PPSI total score, subject's VAS assessment for PPP symptoms (pruritus and pain/discomfort), and DLQI total score.

Protocol Number: 20200195

Date: 15 April 2022 Page 12 of 99

 The IEs are IP discontinuation due to lack of efficacy, adverse event, or use of protocol prohibited medication. The baseline value will be assigned to the data after any of the IEs through week 16 regardless of the observed data.

• The summary measure is the mean difference in change from baseline.

The data where the baseline value is assigned for the treatment failures will be used for the analysis model based on the assumption of missing at random (MAR) (eg, mixed-effect model for repeated measures (MMRM).

Overall Design

This is a phase 3, multicenter, randomized, double-blind, placebo-controlled study evaluating the efficacy and safety of apremilast 30 mg BID versus placebo in Japanese subjects with PPP. During the double-blind placebo-controlled study period, subjects will be randomized 1:1 to apremilast 30 mg BID or placebo for 16 weeks. During the active treatment period, all subjects will receive apremilast 30 mg BID from week 16 through week 52. Following the last treatment dose, subjects will enter a **30-day** observational safety follow-up period. The total study duration per subject is **approximately** 60 weeks. Randomization will be stratified by a subject's rounded PPPASI total score (≤ 20 / 21-30/ ≥31) at baseline and baseline focal infection status (yes/no).

Number of Subjects

Approximately 170 subjects will be randomized in this study.

Summary of Subject Eligibility Criteria

Eligible Japanese subjects must be \geq **18** years of age with PPP diagnosed at least **24 weeks** prior to screening, have a PPPASI total score \geq 12, a PPPASI severity score \geq 2 for pustules/vesicles on palms or soles at screening and baseline, and an inadequate response to topical treatment therapy.

For a full list of eligibility criteria, please refer to Section 5.1 to Section 5.2.

Treatments

During the double-blind placebo-controlled period of the study, all IP will be provided in blister cards. Apremilast will be provided as 10, 20, and 30 mg tablets in the titration cards. Placebo will be provided by the Sponsor as identically appearing 10, 20, and 30 mg tablets.

Protocol Number: 20200195

Date: 15 April 2022 Page 13 of 99

During the active treatment period, apremilast will be provided as 10, 20, and 30 mg tablets in titration cards and 30 mg will be provided in bottles containing 80 tablets after titration. Apremilast will be taken orally BID without food or drink restrictions. To mitigate potential gastrointestinal side effects, dose titration will be implemented in a blinded manner during the first week of the study and during week 16 for subjects initially randomized to placebo who are switching to apremilast 30 mg BID treatment.

Dose modifications outside of the doses described above are not permitted in this study.

Statistical Considerations

Sample Size Considerations

The sample size estimation is based on the results of the phase 2 study (CC-10004-PPP-001 [20200055]). Assuming that a proportion of subjects achieve PPPASI-50 response of 40% and 65% at week 16 for the placebo group and the apremilast 30 mg BID group, respectively, a sample size of approximately 170 subjects in total (85 subjects per group) provides 90% power using a chi-square test with a 2-sided alpha of 0.05. A dropout rate of 5% is anticipated during the double-blind placebo-controlled period of the study.

Planned Analyses

The primary analysis will be performed after all subjects have completed the week 16 visit (visit 8) or have been discontinued from the study. An additional analysis will be conducted after all subjects have completed the week 24 visit (visit 10) or have been discontinued from the study. At the end of the study, after all subjects have either completed the study or been discontinued, the final analysis will be performed. The efficacy analyses will be performed on the ITT population.

The primary endpoint is the achievement of PPPASI-50 at week 16. Subjects who discontinued treatment prior to week 16 (due to lack of efficacy, an adverse event, or protocol deviation due to prohibited medication usage) will be considered as treatment failures and non-responders in the primary analysis. Missing values of the data in which the treatment failures are considered as non-responders will be imputed using multiple imputation (MI).

The treatment difference between the apremilast 30 mg BID group and the placebo group will be analyzed using the Cochran–Mantel–Haenszel (CMH) test, adjusting for the stratification factor at randomization. The 2-sided p-value from the CMH test, the adjusted treatment difference in proportion using the weighted average of the treatment

Protocol Number: 20200195

Date: 15 April 2022 Page 14 of 99

differences across the strata, and the associated 2-sided 95% CI will be provided. The statistical test will be 2-sided at the significance level of alpha = 0.05.

Secondary efficacy endpoints, such as the PPPASI total score change from baseline at week 16, will be analyzed using the mixed-effect model for repeated measures (MMRM) with treatment group, visit time, treatment-by-time interaction, and stratification factors as fixed effects, and the baseline value as a covariate.

To control the overall Type I error rate at the 0.05 level (2-sided) for comparisons between the apremilast 30 mg BID group and the placebo group, a fixed-sequence testing procedure will be applied for efficacy endpoints. Secondary efficacy endpoints will be statistically tested in the following order (change from baseline at week 16) if the primary analysis result is statistically significant:

- 1. PPPASI total score
- 2. PPSI total score
- 3. Subject's VAS assessment for PPP symptoms (pruritus)
- 4. Subject's VAS assessment for PPP symptoms (pain/discomfort)
- 5. DLQI total score

Further sequence will be prespecified in the statistical analysis plan (SAP) prior to the week 16 database lock.

For a full description of statistical analysis methods, please refer to Section 9.

Statistical Hypotheses

Null Hypothesis

The treatment effect of apremilast 30 mg BID and placebo is equivalent.

Alternative Hypothesis

There is a difference in treatment effect between apremilast 30 mg BID and placebo.

Sponsor Name: Amgen Inc.

[figure not shown]

Protocol Number: 20200195

Date: 15 April 2022 Page 15 of 99

1.2 Study Schema

Figure 1-1. Study Schema

BID = twice daily; PPPASI = Palmoplantar Pustulosis Area and Severity Index; W = week

Protocol Number: 20200195

Date: 15 April 2022 Page 16 of 99

1.3 Schedule of Activities

Table 1-1. Schedule of Activities

	Screening		Doul	ole-blind, _l	olacebo-co	ontrolled p		Safety follow-up ^a						
Visit Number	1	2 ^b (Baseline)	3	4	5	6	7	8	9	10	11	12	13/ET	14
Week	- 4 to 0	0	2	4	6	8	12	16	20	24	32	44	52	30 Days after last dose
Allowance (days)	-	+ 2	± 2	± 2	± 2	± 2	± 2	± 2	± 4	± 4	± 4	± 4	± 4	+7
GENERAL AND SAFE	TY ASSESSM	ENTS			•						•	•	•	
Informed consent ^c	X													
Inclusion / Exclusion criteria	Х													
Demographics	Х													
Complete medical history ^d	Х													
Disease history ^e	Х													
Dental examination ^f	Х													
Status of smoking ^g	Х	Х											х	
Prior / concomitant medications and procedures ^h	Х	Х	Х	Х	х	х	х	Х	х	х	х	Х	х	Х
Adverse events		Х	Х	Х	Х	Х	Х	Х	Х	Х	Х	Х	Х	Х
Serious adverse events	Х	Х	Х	Х	Х	Х	Х	Х	Х	Х	Х	х	Х	Х
Psychiatric evaluation ⁱ	X	х	Х	X	х	Х	Х	Х	х	х	х	х	Х	Х

Page 1 of 3

Footnotes are defined on the last page of this table

Protocol Number: 20200195

Date: 15 April 2022 Page 17 of 99

Table 1-1. Schedule of Activities

	Screening		Doub	ole-blind,	placebo-co	ontrolled p		Safety follow-up ^a						
Visit Number	1	2 ^b	3	4	5	6	7	8	9	10	11	12	13/ET	14
		(Baseline)												
Week	- 4 to 0	0	2	4	6	8	12	16	20	24	32	44	52	30 Days after last dose
Allowance (days)	-	+ 2	± 2	± 2	± 2	± 2	± 2	± 2	± 4	± 4	± 4	± 4	± 4	+7
GENERAL AND SAFE	TY ASSESSM	ENTS												
Pregnancy test and contraception education for females of childbearing potential j	х	Х						х					x	
Vital signs ^k	Х	X	Х	Χ	X	Х	X	X	Х	X	Х	Х	Х	Х
Height ^I	Х													
Weight ^I	Х	Х	Х	Х	Х	Х	Х	Х	Х	Х	Х	Х	Х	Х
Complete physical examination m	Х							х					Х	
Limited physical examination ⁿ		Χ°	х	Х	х	Х	х		х	х	Х	Х		x
LABORATORY ASSES	SSMENTS													
Hepatitis B and C ^p	X													
Clinical laboratory evaluations (Hematology/ Chemistry/Urinalysis) ^p	Х	Х				х		Х		Х	Х		Х	×
Urine Drug Screening ^p	Х	Х												
EFFICACY ASSESSMI	ENTS													
PPPASI ^q	х	Х	Х	Х	Х	Х	Х	Х	Х	Х	Х	Х	Х	Х

Page 2 of 3

Footnotes are defined on the last page of this table.

Protocol Number: 20200195

Date: 15 April 2022 Page 18 of 99

Table 1-1. Schedule of Activities

	Screening	placebo-co		Safety follow-up ^a										
Visit Number	1	2 ^b	3	4	5	6	7	8	9	10	11	12	13/ET	14
		(Baseline)												
Week	- 4 to 0	0	2	4	6	8	12	16	20	24	32	44	52	30 Days after
Allowance (days)	-	+ 2	± 2	± 2	± 2	± 2	± 2	± 2	± 4	± 4	± 4	± 4	± 4	+7
EFFICACY ASSESSM	ENTS													
PPSI ^r		Х	Х	Х	Х	Х	Х	Х	Х	Х	Х	Х	Х	Х
SUBJECT REPORTED	OUTCOMES	/ QUALITY O	F LIFE											
Subject's VAS assessment for PPP symptoms for palms and soles ^t		x	Х	Х	х	х	х	х		х	х		х	Х
DLQI ^u		Х				Х		Х		Х	Х		Х	
PHARMACOKINETIC	ASSESSMENT	rs												
BIOMARKER ASSESS	SMENTS													
STUDY TREATMENT														
Randomization (IRT)														
		X												
Dispense IP Return and count IP		Х		Х		Х	Х	Х	Х	Х	Х	Х		
tablets (IP accountability)				X		X	×	X	X	X	х	х	х	

Page 3 of 3

Protocol Number: 20200195

Date: 15 April 2022 Page 19 of 99

BID = twice daily; ET = End of Treatment; IP = investigational product; PAO = pustulotic arthro-osteitis; PPASI = Palmoplantar Pustulosis Area and Severity Index; PPSI = Palmoplantar Pustulosis Severity Index

- a. Subjects who discontinue treatment with IP or withdraw during the active or placebo-controlled treatment period will be asked to enter the 30-day safety follow-up period after the ET visit. Once the study has ended, the investigator will report to Amgen any serious adverse event(s) suspected to be related to the investigational product that he becomes aware of. Refer to Section 8.4.4 for additional details.
- b. Visit 2 is Day 1 (Week 0) and the baseline for all efficacy assessments. All assessments should be conducted prior to the first administration of IP.
- Written informed consent will be obtained by the Principal Investigator or designee prior to performing any study assessments.
- d. A complete medical history starting within 5 years prior to screening must be taken.
- e. Disease history will capture the following information: specific information regarding diagnosis, presence or absence of focal infection (eg, periapical pathosis, periodontitis, angina, and sinusitis), presence or absence of PAO, and presence or absence of PPP with nail.
- Dental examination must be conducted by a dentist during screening period, with data obtained if there is any or no dental focal infection (eg, chronic periapical periodontitis, chronic marginal periodontitis), to evaluate the necessity of treatment (any endodontic treatment for periapical pathosis [eg, infected root canal treatment, tooth extraction], and periodontal surgery for moderate to severe periodontitis). Investigators should evaluate whether a treatment for dental focal infections is preferred to study enrollment. Focal infection status will be confirmed at baseline.
- 9. Smoking history (years/ amount) and current status (yes/no and average number of packs/day).
- h. Inadequate response to any topical treatment should be confirmed.
- At any time when suicidal thoughts or suicide attempt is identified, evaluate the need for referral to psychiatrist and other actions, including discontinuations, as required in Section 8.4.3.
- J. See Section 11.5.
- k. See Section 8.4.1.
- See Section 8.2.5.
- m. See Section 8.2.4.
- A limited physical exam may be performed to evaluate an adverse event or for any reason at the discretion of the Investigator
- Presence of PAO and focal infection status will be assessed during the limited physical examination at baseline.
- q. See Section 11.8.
- See Section 11.9.
- Worst status between visit in which an assessment is scheduled and the previous visit should be recorded. Indicated assessments should be performed for any tests, procedures, or consultations (PPPASI, PPSI, and for palms and soles) for that visit. See Section 11.11.

Protocol Number: 20200195

Date: 15 April 2022 Page 20 of 99

2. Introduction

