7.1 Discontinuation of Study Treatment

Subjects (or a legally authorized representative) can decline to continue receiving investigational product and/or other protocol-required therapies and/or procedures at any time during the study but continue participation in the study. If this occurs, the investigator is to discuss with the subject the appropriate processes for discontinuation from investigational product or other protocol-required therapies and must discuss with the subject the possibilities for continuation of the Schedule of Activities (see Table 1-1) including different options of follow-up (eg, in person, by phone/mail, through family/friends, in correspondence/communication with other treating physicians, from the review of medical records) and collection of data, including endpoints, adverse events, and must document this decision in the subject's medical records. Subjects who have discontinued investigational product and/or other protocol-required therapies and/or procedures should not be automatically removed from the study. Whenever safe and feasible, it is imperative that subjects remain on-study to ensure safety surveillance and/or collection of outcome data.

Reasons for early removal from protocol-required investigational product(s) or procedural assessments may include any of the following:

- decision by Sponsor
- lost to follow-up
- death
- adverse event
- subject request
- lack of efficacy
- protocol deviation
- pregnancy

Protocol Number: 20200195

Date: 15 April 2022 Page 41 of 99

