8.1.3 Safety Follow-up

Upon permanent discontinuation from the study treatment for any reason, a safety follow-up visit will be performed approximately **30 days** (+ **7** days) after the end of the last dose of apremilast.

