2.1 Objectives and Endpoints/Estimands

Objec	tives	Endpoints			
Prima	Primary				
•	To evaluate the efficacy of apremilast 30 mg twice daily (BID) compared with placebo in subjects with PPP	 Achieving at least 50% reduction from baseline in Palmoplantar Pustulosis Area and Severity Index (PPPASI) total score (PPPASI-50) at week 16 			
Seco	ndary				
•	To evaluate the efficacy of apremilast 30 mg BID compared with placebo in subjects with PPP	 Change from baseline in PPPASI total score at week 16 Change from baseline in Palmoplantar Pustulosis Severity Index (PPSI) total score at week 16 Change from baseline in subject's Visual Analogue Scale (VAS) assessment for PPP symptoms (pruritus and pain/discomfort) at week 16 Change from Baseline in Dermatology Life Quality Index 			
		(DLQI) total score at week 16			
•	To evaluate the safety and tolerability of apremilast 30 mg BID compared with placebo in subjects with PPP	 Treatment-emergent adverse events (TEAEs), serious TEAEs, and TEAEs of interest Clinically significant changes in body weight, vital signs, and laboratory abnormalities 			

Primary Estimand

The main estimand of primary interest for the primary efficacy endpoint (i.e., achievement of PPPASI-50 response defined as at least 50% reduction from baseline in PPPASI total score, at week 16) is defined in terms of the following attributes:

- The target population of interest is Japanese subjects with PPP defined through the inclusion/exclusion criteria.
- The primary endpoint is the achievement of PPPASI-50 response at week 16.
- Intercurrent events (IEs) are investigational product (IP) discontinuation due to lack of efficacy, adverse event, or protocol-prohibited medication use. A subject will be considered a treatment failure after any of the IEs.
- The summary measure is the difference between apremilast 30 mg BID group and placebo group in proportion of responders based on the intent-to-treat (ITT) population including all randomized subjects.

A missing value after any of the IEs will be imputed as non-responders, otherwise, will be imputed with a multiple imputation (MI) method. A non-missing value after any of the IEs will also be imputed as non-responders.

Secondary Estimand(s)

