5.5 Analysis Phases

• Placebo-controlled Phase/Period – Weeks 0 to16

This period starts on the day of randomization (Week 0/Visit 2), and stops on below:

(1) the day of Week 16/Visit 8 if the subject continued study treatment to the active treatment phase

(2) the day of the discontinuation if the subject discontinued study treatment prior to or at Week 16/Visit 8

(3) the last known study day if the subject is lost to follow-up prior to or at Week 16/Visit 8

• Active Treatment Phase/Period – Weeks 16 to 52

This period starts on one day after the day of the dose of apremilast distributed at Week 16/Visit 8, and stops on either below.

(1) the day of Week 52/Visit 13

(2) the day of the discontinuation if the subject discontinued prior to or at Week 52/Visit13

(3) the last known study day if the subject lost to follow-up prior to or at Week 52/Visit 13 during the phase

For safety analysis, the period starts on the day of the first dose of apremilast in the period.

• Safety Follow-up Phase/Period

Subjects who complete or discontinue the study treatment, will be followed up for 30 days after the end of treatment visit.

For adverse event analysis, data from the first 30 days after the last dose of IP will be included in the precedent treatment phase and data after the 30 days will be presented separately.

• Apremilast exposure period

This period starts on the date of either:

- the first dose of IP following randomization (Week 0/Visit 2) for subject who are treated with apremilast from Week 0

- the first dose of IP from the IP dispensed at Week 16/Visit 8 for subjects who were originally treated with placebo and are switched to apremilast at Week 16

This period stops on either: (1) data restriction date; or (2) the end of the study.

During the apremilast-exposure period, data are presented by treatment sequence, i.e., Placebo/30 mg BID, 30 mg BID as Initiated, and a total column of 30 mg BID as Treated.

6. Populations for Analysis

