9.2 Subject Accountability

Frequency summary of subjects randomized, screened but not randomized among all screened subjects will be provided. The frequency of subjects who failed each inclusion/exclusion criteria will be included in the summary.

The number and percentage of subjects included in the ITT and safety analysis population will be summarized.

Subject disposition will be provided for placebo-controlled period and active treatment period based on ITT population respectively. Summary of safety follow-up period and study completion will be included in each disposition summary. The summaries include the number and percentage of subjects who entered the period, who completed the period, who completed IP, who ended IP and study with the reason. Subjects who ended IP are considered to enter the safety follow-up period unless the subjects ended the study on the same day.

Key study dates for the first subject screened and enrolled (randomized), last subject enrolled (randomized), data cut-off (last subject's week 16 and 24 visit), last subject end of IP, last subject end of study will be presented.

The number and percentage of subjects randomized will be tabulated by study site.

Listings of subject accountability will be provided.

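### The route after stopping investigational product (Table 1-1 footnote a, Section 8.1.3, SAP 5.5) is not reconciled with Section 7.1, so week-16 efficacy values of some non-intercurrent-event stoppers may be lost or go unused

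*Protocol*

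**What the plan says.** **Route after stopping IP.** Protocol Table 1-1, footnote a, covers subjects who discontinue IP or withdraw in either treatment period. They "will be asked to enter the 30-day safety follow-up period after the ET visit". Protocol Section 8.1.3 agrees: "Upon permanent discontinuation from the study treatment for any reason, a safety follow-up visit will be performed", about 30 days (+7) after the last dose. SAP 5.5 has: "Subjects who complete or discontinue the study treatment, will be followed up for 30 days after the end of treatment visit". SAP 9.2 counts subjects accordingly in the disposition tables: "Subjects who ended IP are considered to enter the safety follow-up period unless the subjects ended the study on the same day".

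**Retention.** Protocol Section 7.1 treats stopping IP as different from leaving the study. Stoppers are not to be removed automatically, the investigator "must discuss with the subject the possibilities for continuation of the Schedule of Activities", and "Whenever safe and feasible, it is imperative that subjects remain on-study to ensure safety surveillance and/or collection of outcome data".

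**Estimand.** SAP 2.1 defines: "Intercurrent events (IEs) are investigational product (IP) discontinuation due to lack of efficacy, adverse event, or protocol-prohibited medication use". For the primary endpoint, "A non-missing value after any of the IEs will also be imputed as non-responders". For the secondary endpoints the baseline value is assigned after such an event, whatever was observed. PPPASI missing for other reasons is multiply imputed (SAP 9.5.1). Other missing secondary data are left to the MMRM under missing at random (SAP 9.5.2).

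**The concern.** A site that looks up what to do when a subject stops IP finds an ET visit and a safety visit in the schedule, and no column for continued efficacy visits off treatment. Section 7.1 asks for continuation to be discussed but refers back to that same table. The introduction to Section 8 requires adherence to the schedule, so a site could reasonably take the footnote as the whole instruction.

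Section 7.1 also lists stop reasons that are not intercurrent events: subject request, sponsor decision, pregnancy, and protocol deviations other than prohibited medication. For these subjects a week-16 measurement is informative. If it is not taken, the primary endpoint is filled in by a model fitted largely to subjects still on treatment. That could overstate response in the arm with more such stops. The secondary endpoints rest on the same assumption, and Table 9-2 of the SAP rules out sensitivity analyses for them.

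**Working it through.** **1. The plan's own figure.** Inputs (Protocol Section 9.2, SAP 3.2): 40% vs 65%, 85 per arm, two-sided alpha 0.05, chi-square test. With the pooled variance under the null and p̄ = 0.525:

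Power = Φ{[0.25·√85 − 1.960·√(2·0.525·0.475)] / √(0.40·0.60 + 0.65·0.35)} = Φ{(2.305 − 1.384)/0.684} = Φ(1.347) = 91.1%.

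This reproduces the stated 90%.

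**2. Who is affected.**

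| Reason for stopping IP before week 16 | Is a collected week-16 value used? |
|---|---|
| Lack of efficacy, adverse event, prohibited medication | No. Non-response or baseline value is assigned regardless |
| Subject request, sponsor decision, pregnancy, other deviation | It should be. If missing: imputation or MMRM |
| Death, lost to follow-up, withdrawn consent | Cannot be collected |

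Only the second row is at issue.

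**3. Timing under footnote a.** Week 16 is day 16 × 7 + 1 = 113, and the ±2-day allowance gives days 111–115. Visit 14 falls 30 to 37 days after last dose day L.

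- It can reach day 111 only if L ≥ 111 − 37 = 74.
- It can be as early as day 115 only if L ≤ 115 − 30 = 85.

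A subject with L before about day 74 therefore finishes before the week-16 allowance. With L from about 74 to 85, visit 14 may happen to fall in it. With a later L, visit 14 falls after it. Visit 14 includes PPPASI, PPSI and VAS but not DLQI.

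**4. Whether a collected value would be used.** SAP 5.5 ends the placebo-controlled period on the day of discontinuation. The week-16 windows visible in SAP Appendix B run from day 100 (VAS) or day 86 (DLQI) to the end of that period. A week-16 value taken after an earlier stop therefore falls outside the period and may not be assigned to week 16. No window table for PPPASI or PPSI is visible in the public text, possibly because it was removed, so this step rests on SAP 5.5 and the visible tables.

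**5. Size.** Dropout of 5% gives 0.05 × 170 = 8.5 subjects, or 4.25 per arm. The non-intercurrent-event share f is not given, so it is ranged over 0–100%. One value is worth at most 1/85 = 1.2 points of an arm's response rate, and 4.25 values at most 4.25/85 = 5.0 points.

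For power, intercurrent-event stoppers are counted as non-responders, so each arm's rate is p × [1 − 0.05(1 − f)]. Other stoppers are assumed to respond at their arm's rate. Values observed means n = 85 per arm. Values lost means n = 85(1 − 0.05f), which ignores everything imputation recovers.

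| f | Values concerned | Power, observed | Power, lost |
|---|---|---|---|
| 0% | 0 | 87.9% | 87.9% |
| 25% | 2.1 | 88.7% | 88.4% |
| 50% | 4.25 | 89.6% | 88.8% |
| 75% | 6.4 | 90.3% | 89.2% |
| 100% | 8.5 | 91.1% | 89.6% |

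The largest cost is 91.1 − 89.6 = 1.5 points.

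**The case against.** A reader might infer that the schedule sends every stopper out of efficacy follow-up, that sites will never obtain the week-16 PPPASI, and that the estimand fails without it. The documents do not support that reading.

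- Footnote a says subjects are asked to enter safety follow-up. It does not cancel scheduled visits, and a 30-day safety visit can coexist with continued efficacy visits.
- What Section 7.1 calls imperative is staying on-study, conditional on safety and feasibility. Continuing the schedule is only to be discussed.
- PPPASI is taken at both ET and visit 14, and visit 14 can coincide with week 16.
- After the three intercurrent events the estimand does not use an observed value.
- SAP 9.2 is a counting rule for disposition tables. It does not instruct sites.

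The primary endpoint also has safeguards. Imputation conditions on treatment, stratification factor and the subject's own earlier scores, and non-responder imputation and a tipping-point analysis are planned (SAP 9.5.1). The 1.2 points per subject is a ceiling: if imputation tracks the planned 65%, three true non-responders on apremilast shift that arm by 3 × 0.65/85 = 2.3 points, not 3/85 = 3.5. Some of the 5% will also have withdrawn or been lost, and no footnote recovers them.

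All of this stands, and it keeps the point small. It does not reconcile the passages. The safeguards examine the effect of missing data without recovering any, and the secondary endpoints have none.

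**Conclusion.** The protocol gives two accounts of what follows IP discontinuation, and the schedule supports only one of them. They must be reconciled. The consequence is confined to subjects who stop before week 16 for reasons outside the three intercurrent events and who would agree to be seen again. At the planned dropout that is somewhere between none and 8.5 of 170, with a power cost of about 1.5 points or less. The result of the trial is unlikely to turn on it.

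Three assumptions carry these figures: that the undefined 5% dropout approximates stops before week 16, that the share of other reasons is unknown, and that such subjects respond at their arm's rate. A higher discontinuation rate would scale the count up. If off-treatment response is lower, the issue is bias more than power, limited by the per-subject ceiling above.

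Collection alone may not be enough. Unless SAP 5.5 changes, a week-16 value obtained under Section 7.1 may be left out and imputed instead.

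**What to change.** - **Protocol, Table 1-1 footnote a:** state that subjects who stop IP before week 16 and agree to stay continue the scheduled PPPASI, PPSI, VAS and DLQI assessments through week 16, in addition to the ET and 30-day safety visits. Cross-refer to Section 7.1. The safety visit stays as Section 8.1.3 describes for everyone, including those who decline efficacy visits.
- **SAP 5.5 and Appendix B:** amend the end of the placebo-controlled period, and the week-16 windows tied to it, for efficacy data. An observed week-16 value from a subject who stopped for a reason other than an intercurrent event is then assigned to week 16 and analysed, not imputed. The handling of the three intercurrent events does not change.
- **SAP 9.2:** no change in substance. A note that a subject can be in safety follow-up and still attend efficacy visits would avoid confusion.

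The cost is a few sentences in each document and a few already-scheduled visits for a handful of off-treatment subjects. Week-16 values that are not collected cannot be recovered later.
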